3.2. Sample Size

The sample size, as conceived in the original protocol, was based on the second primary efficacy variable. A sample size of 162 efficacy evaluable patients would provide 80% power for a two-sided 95% CI that is completely above 50% for the second primary efficacy variable of effective hemostasis, demonstrating a response rate above 50% for that variable. This is based on an anticipated response rate of 61%.

Also, it was estimated that ~30% of the safety population will have anti-fXa activity < 75 ng/mL (0.25 IU/mL for patients receiving enoxaparin) and therefore will not be included in the primary analysis. Additionally, it is estimated that up to 5% of patients will be non-evaluable for reasons unrelated to andexanet. Given these factors, the original sample size of the study was set to 250 patients. With the implementation of Protocol Amendment 4 (per a request from the FDA to enrich the enrolled population with ICH patients), enrollment was to continue until at least 110 evaluable ICH patients were enrolled to more comprehensively capture clinical outcomes in this high risk patient population. Therefore, to accommodate this request, the sample size was increased to a total enrollment of 350 patients.

With the implementation of Protocol Amendment 6, the final sample size was adjusted based on changes in enrollment strategy for various bleed types and FXa inhibitors, a need to meet regulatory requirements for sufficient numbers of patients for each FXa inhibitor and/or geographic region, or new information from registries, observational studies, clinical trials, and/or other sources. To accommodate a potential increase in sample size based on these factors, the overall enrollment was increased to 500 patients.

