Effective hemostasis will be further defined as:

- 0 = patients with hemostatic efficacy rated by the EAC as poor/none
- 1 = patients with hemostatic efficacy rated by the EAC as excellent or good.
- 2 = Not evaluable due to non-administrative reason
- 3 = Not evaluable due to administrative reason.

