5.0 STATISTICAL METHODS

5.1. General Considerations

All hypothesis tests will be 2-sided and reported at the 0.05 significance level. All CIs will be 2-sided and reported at the 95% confidence level unless stated otherwise. P-values will be rounded to 3 decimal places. P-values less than 0.001 will be presented at p < 0.001.

For continuous variables, the number of non-missing observations, mean, median, quartiles, standard deviation, minimum, maximum, and 95% confidence interval (CI) will be presented unless stated otherwise. Means, medians, quartiles, and 95% CI will be displayed to 1 more decimal place than the raw data and the standard deviation will be displayed to 2 more decimal places. The minimum and maximum will be displayed to the same number of decimal places as reported in the raw data. For categorical variables, the number of observations, the number of events, and percentages of events with the 95% CI will be reported. Descriptive summaries will be presented for the efficacy population as well as for the individual subgroup analyses.

It is anticipated that all statistical analyses will be performed using SAS Version 9.4 (SAS Institute, Inc., Cary NC) or higher. Additional software may be used for the production of graphics and for statistical methodology not provided by SAS. All summaries and analyses documented in this Statistical Analysis Plan (SAP) will be presented in the final integrated CSR. The CSR may also contain additional tables or statistical tests as warranted by the data obtained. The justification for any such additional analyses will be fully documented in the CSR.

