5.5.2. Hemostatic Efficacy

For primary efficacy analysis, missing values (i.e., rated as Non-Evaluable due to administrative reasons) will be excluded from analysis. On the other hand, missing values due to non-administrative reason will be considered as treatment failure.

Non-evaluable for administrative reason is defined in the EAC Charter. The final decision regarding whether a patient is non-evaluable due to administrative or non-administrative reasons will be made by the EAC.

A sensitivity analysis will be performed with all patients rated as Non Evaluable classified as not reaching hemostatic efficacy.

5.5.3. **NIHSS**

Analysis will be performed only for the baseline and 12 hours post treatment. If the baseline or the 12-hour post-treatment NIHSS score is missing, the patient will be excluded from analysis.

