5.13.1. Primary Efficacy Analysis

Two primary endpoints will be evaluated:

- The percent change from baseline in anti-fXa activity to the on treatment nadir (i.e., minimum value between EOB and EOI).
- The achievement of hemostatic efficacy of stopping an ongoing major bleed at 12 hours from the end of the andexanet infusion, rated by the independent EAC as excellent or good.

The first objective is to demonstrate the decrease in anti-fXa activity following and examet treatment. Analysis will include all patients in the efficacy population. The following hypothesis will be evaluated:

Ho:
$$\mu = 0$$

H₁:
$$\mu \neq 0$$

The percent change in anti-fXa activity from baseline (last measurement before administration of andexanet) to post administration (the lowest level measured between the start of andexanet administration and 10 minutes after the end of the andexanet administration) will be calculated for each patient as %change = $100 \times (post - baseline)$ / baseline rounded to 1 decimal place. Percent change from baseline in anti-fXa activity will be evaluated using a distribution free two-

sided 95% CIs for the median. Because the data are expected to be non-normal, the distribution free confidence interval will be the primary for decision making. If the CI for the median excludes 0, the first primary objective will be considered to have been met. The CI will be calculated using distribution free methods using PROC UNIVARIATE in SAS as shown below.

```
proc univariate ciquantdf (alpha=.05);
var val;
ods output Quantiles=results;
run;
```

The second primary objective is to evaluate the hemostatic efficacy following and exanet treatment. Analysis will be performed including all patients in the efficacy population with valid EAC hemostatic efficacy adjudication (excluding events adjudicated as non-evaluable due to administrative reason). In addition, a sensitivity analysis will be conducted with the patients adjudicated as non-evaluable due to administrative reason rated as poor hemostatic efficacy.

The following hypothesis will be evaluated:

```
H_0: \pi = 0.50
```

 H_1 : $\pi \neq 0.50$

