The proportion of patients in the Efficacy Analysis Population who are adjudicated to have effective hemostasis (excellent or good) by the independent EAC will be summarized. An exact 95% CI will be reported. The study will be considered to have met its second primary efficacy objective if the proportion of patients with excellent or good hemostasis (as adjudicated by the independent Endpoint Adjudication Committee [EAC]) is statistically significantly higher than 50% (p < 0.05). This test will be performed by calculating the exact binomial confidence interval and checking that it only contains points above 0.5. In addition to the confidence interval the one sided (right) p-value from the exact binomial test that the lower bound of the confidence interval will be higher than 50% will be presented. In SAS this will use the exact binomial option in PROC FREQ as shown below.

```
proc freq;
tables val binomial (p=.50) noprint;
exact binomial;
output out=results binomial exact;
run;
```

To maintain the type I error rate, the decision on the second primary objective will only be made if the first primary objective is met. This results in a fixed sequence multiple comparisons procedure.

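### The SAS step printed for the second primary objective names no response level, so on the SAP's own 0/1 coding it would by default report the exact interval for poor/none hemostasis instead of excellent/good.

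*SAP*

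**What the plan says.** SAP 4.3 defines effective hemostasis as a four-level variable. It starts with "0 = patients with hemostatic efficacy rated by the EAC as poor/none", gives 1 to excellent or good and 2 to patients not evaluable for a non-administrative reason, and ends with "3 = Not evaluable due to administrative reason".

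SAP 5.5.2 sets the rules for the non-evaluable codes. Administrative cases are left out of the primary analysis, while "missing values due to non-administrative reason will be considered as treatment failure". SAP 5.13.1 repeats the exclusion for the second primary objective ("excluding events adjudicated as non-evaluable due to administrative reason") and assigns the version that counts these patients as poor to a sensitivity analysis.

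SAP 5.13.1 then gives the success rule: the exact binomial interval for the excellent-or-good proportion must lie wholly above 0.5. It says that the test will be run in PROC FREQ and prints the step. The operative line is "tables val binomial (p=.50) noprint", followed by an exact-binomial request and an output statement. The step shows no LEVEL= option, input data set, WHERE clause or recode.

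**The concern.** Without a LEVEL= option, the BINOMIAL option analyses the first level of the variable. Under the only coding in the SAP, that level is 0, poor/none. The same holds for the four-level variable, for that variable with code 3 removed, and for any 0/1 recode that keeps 1 as success. The printed interval would then describe the wrong outcome, and it is the interval on which the objective is decided.

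A second gap lies beside it. The test needs a binary response, but the SAP never writes out how the four codes become one. The rules can be assembled from 5.5.2 and 5.13.1, but the code does not carry them. If the wrong level were noticed only when the output was read, the code for a primary endpoint would be repaired after results had been seen, and the possible repairs do not all give the same answer.

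**Working it through.** **Inputs.** Null rate 0.50 and the exact-interval rule come from SAP 5.13.1. The error rate comes from SAP 5.1: "All hypothesis tests will be 2-sided and reported at the 0.05 significance level". The design comes from SAP 3.2: "A sample size of 162 efficacy evaluable patients would provide 80% power for a two-sided 95% CI", and "This is based on an anticipated response rate of 61"%. Codes 0 to 3 come from SAP 4.3. SAP 3.2 expects up to 5% of patients to be non-evaluable but does not split them between codes 2 and 3, so the counts for those codes below are illustrative.

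**Step 1: reproduce the plan's figure.** The exact (Clopper-Pearson) 95% interval for x of n has lower limit equal to the 0.025 quantile of Beta(x, n−x+1) and upper limit equal to the 0.975 quantile of Beta(x+1, n−x). With n = 162, the lower limit first exceeds 0.5 at x = 94 (94/162: 0.5003; 93/162: 0.4941). The one-sided error is P(X ≥ 94 | 162, 0.50) = 0.0246, and power is P(X ≥ 94 | 162, 0.61) = 0.805. The smallest n with at least 80% power is 162, so the plan's figure is confirmed.

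**Step 2: planning case on binary data.** 0.61 × 162 = 98.8, so take 99 effective and 63 failures.

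| Quantity | Count | Rate | Exact 95% CI | Interval above 0.5? |
|---|---|---|---|---|
| Intended (level 1) | 99/162 | 61.1% | 53.1 to 68.7% | yes |
| Default level (level 0) | 63/162 | 38.9% | 31.3 to 46.9% | no |

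The two intervals are exact complements. The lower tail for 63/162, P(X ≤ 63 | 162, 0.5) = 0.0029, equals the intended upper tail, P(X ≥ 99 | 162, 0.5) = 0.0029, by symmetry at 0.5. If the software reports the tail on the side of the observed deviation, the one-sided p-value would look right while the interval was wrong. At a true effective rate of 61%, the chance that the level-0 interval meets the rule is P(X ≥ 94 | 162, 0.39) = 7.6 × 10⁻⁷.

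**Step 3: code 2 not recoded.** Let 5 of the 63 failures carry code 2, leaving 58 at code 0. With code 3 already removed, the default gives 58/162 = 35.8% (28.4 to 43.7%). Its complement is 64.2%, not 61.1%, so subtracting the printed result from 1 is not a safe repair. With 8 code-3 rows also present, it gives 58/170 = 34.1% (27.0 to 41.8%).

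**Step 4: LEVEL='1' added but code 3 left in.** With 99 effective and 162 analysable patients plus k administrative cases, the denominator is 162 + k:

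- k = 8: 99/170 = 58.2%, CI 50.4 to 65.7%
- k = 9: 99/171 = 57.9%, CI 50.1 to 65.4%
- k = 10: 99/172 = 57.6%, lower limit 49.8%

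The decision in the planning case therefore reverses at 10 such rows, which is 10/172 = 5.8% of rows. With 9 rows (9/171 = 5.3%), at least 99 successes are needed instead of 94, and power is P(X ≥ 99 | 162, 0.61) = 0.523, down from 0.805.

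**The case against.** The best answer is that the snippet is schematic. Its variable name, `val`, is also used for percent change in the PROC UNIVARIATE step of the same section. No data set is named, and the extracted line has no slash before its options, which may be a loss in reading the PDF and is not counted here. The decision rule is set in prose, and the prose is unambiguous about the proportion, the null value, the interval and the excluded patients. A poor/none rate in the output would also clash visibly with the planned hemostatic-efficacy tables.

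Much of this stands. It disposes of a stronger reading that a reader might infer, namely that the plan keeps administratively non-evaluable patients in the denominator. SAP 5.5.2 and 5.13.1 expressly exclude them, and the filter may be applied before the step. Nor do the documents support saying that the trial would wrongly fail. That would require the output to be read without noticing the level, against the prose rule. The LEVEL='1'-only case in Step 4 is a hypothetical half-repair that would breach the prose, and at 9 administrative cases it still meets the rule.

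The placeholder argument does not remove the level problem. Whichever recode `val` stands for, level 0 is analysed unless success happens to be coded or sorted first, and the SAP nowhere says that it is.

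**Conclusion.** The concern holds as a minor error in the printed code. On the SAP's coding, the step for the second primary objective would by default return the interval for poor/none. In the binary planning case that is 31.3 to 46.9% in place of 53.1 to 68.7%. The step also omits the recode of code 2 and the exclusion of code 3, which the prose requires and which may be done upstream.

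The conclusion rests on two assumptions. The first is that PROC FREQ takes the first sorted level when LEVEL= is absent; this is general software knowledge and was not run in SAS. The second is that success keeps the code 1. The counts for codes 2 and 3 are illustrative. Severity is minor because the prose rule is correct, the error would be visible, and it works against declaring success when the drug does well. It could signal success falsely only if more than half of patients were rated poor/none.

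**What to change.** In SAP 5.13.1, define the analysis variable before the code: RESP = 1 for code 1, RESP = 0 for codes 0 and 2, RESP = missing for code 3. Replace the statement with `tables RESP / binomial(p=0.5 level='1');` and keep the exact-binomial request. For the sensitivity analysis, set RESP = 0 for code 3. Use the same RESP for the subgroup summaries in 5.13.1.2 and the ICH analysis in 5.15.1.6. Name the input data set, and confirm on a small test data set containing all four codes that the output refers to level 1 with the intended denominator.

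The cost is a few lines of SAP text and code. It needs no new data and changes neither the estimand, the sample size nor the decision rule.

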5.13.1.1. Sensitivity Analysis

Sensitivity analyses will be performed for two primary efficacy endpoints for patients who are otherwise efficacy evaluable but have baseline anti-fXa level of less than 75 ng/mL for apixaban and rivaroxaban, less than 40 ng/mL for edoxaban, and less than 0.25 IU/mL for patients receiving enoxaparin.

In addition, the primary efficacy analysis will be performed including all patients in the safety population with anti-fXa level at baseline.

5.13.1.2. Exploratory Analysis

Consistency of efficacy across important subgroups will be investigated. Analysis will be performed for the efficacy population. The two primary endpoints will be summarized for the following subgroups:

- Sex (Male, Female)
- Race (any race with at least 5 members, all other races combined)
- Age (< 65 years, 65–75 years, >75 years)
- FXa inhibitor (apixaban, rivaroxaban, edoxaban, enoxaparin)
- Bleed type (GI, ICH, Other)
- Dose of andexanet (low dose [400 mg bolus + 480 mg infusion], high dose [800 mg bolus plus 960 mg infusion])
- Region (North America, Europe, and Japan)
- Renal function (eGFR < 50 mL/min, eGFR ≥ 50 mL/min)

5.14. Secondary Efficacy Analysis

The secondary objective of the study is to assess the relationship between the change from baseline in anti-fXa activity and achievement of hemostatic efficacy in patients receiving an FXa inhibitor who have acute major bleeding and reduced FXa activity.

Analysis

A logistic regression model predicting the log-odds ratio of success of hemostatic efficacy (rated as "Excellent" or "Good"), with the anti-fXa level activity as a covariate will be used to determine the relationship between anti-fXa level and the clinical outcome.

A subset analysis on the Intracranial patients will be performed using a logistic regression with 2 additional covariates: the log of (the baseline ICH volume + 1), and an indicator variable for baseline Infratentorial involvement.

Anti-fXa Level Measurement

Hemostatic efficacy is achieved when the body has time to produce thrombin and a subsequent clot, thus the anti-fXa level during the first few hours after administration is more important than the decrease in anti-fXa level to predict the log-odds of success of hemostatic efficacy. Therefore, the on-treatment nadir value will be used in the analysis.

Standardization Across Inhibitors

The most power would be gained if it were possible to pool the data across all the anti-fXa inhibitors, however, anti-factor Xa activity levels cannot be combined in the same analysis due to the different bioavailability and pharmacokinetics of the individual FXa inhibitors, especially between the direct and indirect FXa inhibitors. An alternative way to use the activity level that would enable pooling the data is to convert the continuous measurements into a dichotomous variable indicating a level that has similar anticoagulant effects across the 4 different inhibitors.

For the DOACs, current guidelines by the subcommittee on control of anticoagulation of the International Society on Thrombosis and Hemostasis (ISTH) and the French Working group on perioperative hemostasis (GIHP) recommend using a value of 30 ng/mL to determine if antidote administration should be considered.[4, 5] Unfortunately there is no similar threshold for the indirect anticoagulants, therefore the threshold for the Enoxaparin patients in the analysis will be the lower limit of detection (0.10 IU/mL). Sensitivity analyses excluding patients taking Enoxaparin will be performed as well, with (1) the log of anti-fXa at on-treatment Nadir as a covariate, and (2) the dichotomous variable for anti-fXa less than the threshold as a covariate.

A summary of the planned analyses is below:

Model	Population	Reduced Model covariates	Full Model covariates
1	Efficacy, excluding patients with Non-Evaluable Hemostatic Efficacy due to Admin reason	None (intercept only model)	Indicator variable for on- treatment Nadir anti-fXa level < threshold*
2	Same as (1) except exclude Enoxaparin patients also	None (intercept only model)	Indicator variable for on- treatment Nadir anti-fXa level < threshold*
3	Same as (1) except exclude Enoxaparin patients also	None (intercept only model)	Log of on-treatment Nadir anti-fXa level

4	Same as (1) except exclude non-ICH patients also	Log of (baseline ICH volume +1), Indicator	Reduced Model covariates plus Indicator variable for
	non-reri patients also	variable for Infratentorial	on- treatment Nadir anti-
		involvement	fXa level < threshold*

^{*}The threshold=30 ng/mL for Apixaban, Rivaroxaban and Edoxaban, and 0.10 IU/mL for Enoxaparin.

Descriptive statistics, odds ratios with the corresponding 95% confidence intervals, and p-values from the models will be presented. The Full Model will be compared to the Reduced Model with a Likelihood Ratio Test. The Reduced Model will be rejected in favor of the Full Model if the Likelihood Ratio Test p-value is <0.05.

The area under the receiver operating characteristic (AUC under ROC) with the 95% CI will be presented.

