2.2. Secondary Efficacy Objective

• To assess the relationship between decrease in anti-fXa activity and achievement of hemostatic efficacy in patients receiving a FXa inhibitor who have acute major bleeding and reduced FXa activity.

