11.5.2. Primary Efficacy Endpoints

The two primary endpoints are the following:

The percent change from baseline in anti-fXa activity to the nadir from the evaluation period (where the evaluation period starts 5 minutes following the end of the andexanet bolus and ends 10 minutes after the end of the andexanet infusion),

AND

The achievement of hemostatic efficacy.

The primary endpoints, including the evaluation of hemostatic efficacy in specific study populations against specific comparators, will be ordered in a fixed sequence multiple comparisons (i.e., hierarchical) fashion as delineated in the SAP.

11.5.3. Secondary Efficacy Endpoint

The secondary objective is to assess the relationship between the two primary endpoints to establish change in anti-fXa activity as a predictor of achievement of hemostatic efficacy. No additional endpoint is defined to support this objective.

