11.5.6. Statistical Methodology for Endpoint Analyses

The first primary efficacy endpoint, i.e., percent change in anti-fXa activity from baseline (last measurement before administration of andexanet) to nadir (the lowest level measured between 5 minutes prior to the start of andexanet administration and 10 minutes after the end of the andexanet administration) will be calculated for each patient as change = 100 %×(post-baseline)/baseline. Percent change from baseline in anti-fXa activity will be assessed with two-sided 95% CIs. A nonparametric CI for the median will be reported. If the nonparametric CI for the median excludes 0, the first primary objective will be considered to have been met. For the first primary endpoint, patients who do not have at least one anti-fXa activity level within the evaluation period for non-administrative reasons will have percent decrease imputed as 0.0% (i.e., using the baseline value as the nadir value).

The second primary efficacy endpoint, proportion of efficacy evaluable patients who are adjudicated to have effective hemostasis (excellent or good) by the independent EAC will be summarized as a point estimate with an asymptotic 95% confidence interval.

To maintain the type I error rate, the statistical evaluation of the primary endpoints, including the analysis of hemostatic efficacy in specific study populations against specific comparators, will be ordered in a fixed sequence multiple comparisons (hierarchical) procedure.

The secondary endpoint will be assessed by plotting the Receiver Operating Characteristics (ROC) curve and calculating the Area Under the Curve (AUC). Patients will be classified as success or failure based on achievement of hemostatic efficacy. For each potential cut point of a percent change in anti-fXa activity, the sensitivity and specificity of that cut point to distinguish achievement of hemostatic efficacy will be calculated. The ROC plots sensitivity by 1 - specificity. An AUC of 0.5 or lower indicates that the percent change in anti-fXa activity does not predict achievement of hemostatic efficacy. An AUC of 0.7 or higher is indicative of a relationship that is more useful in predicting hemostatic efficacy [27]. The Minimum Clinically Important Difference (MCID) of percent decrease in anti-fXa activity will be derived as the value that simultaneously maximizes sensitivity and specificity.

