1.0 INTRODUCTION

This document details the statistical analyses that will be performed for Portola Pharmaceuticals, Inc. (Portola) Study 14-505 "Prospective, Open-label Study of Andexanet Alfa in Patients Receiving a Factor Xa Inhibitor who have Acute Major Bleeding (ANNEXA-4)". This Statistical Analysis Plan (SAP) is based on ANNEXA-4 Protocol Amendment 6, dated 30 November 2018. Documents related to this SAP are:

- Andexanet alfa (ANNEXA-4) Study 14-505 Protocol Amendment 6, titled "Prospective, Open-label Study of Andexanet Alfa in Patients Receiving a Factor Xa Inhibitor who have Acute Major Bleeding (ANNEXA-4)."
- Data Safety Monitoring Board (DSMB) Charter, Version 2.0, dated 20 October 2015.
- ANNEXA-4/Usual Care Cohort Endpoint Adjudication Committee Charter, Final Version 5.0, dated January 30, 2018.

To support marketing authorization submissions for the Food and Drug Administration (FDA) and European Medicines Agency (EMA), analysis will be performed on all N=477 locked patients in the database.

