4.6.8. Thrombotic Events

Thrombotic events (TE) will be adjudicated by the EAC (see CRF#122). A patient may have multiple Thrombotic events.

- Adjudicated Thrombotic events will be rated as follows:
 - 0 = If the event type is adjudicated as Death or Other AE. These events are not considered to be TEs.
 - 0 1 = If the event type is adjudicated as Myocardial Infarction; Ischemic Stroke (Stroke with adjudicated code of 021 for Ischemic), Transient Ischemic Attack, Deep Vein Thrombosis, Pulmonary Embolism or Arterial Systemic Embolism) and the adjudication decision is "Agree". These events are considered to be TEs.
- Thrombotic Event Type: Defined based on CRF#122 and coded as follows:
 - CVA = Ischemic Stroke
 - o MI = Myocardial Infarction
 - o DVT = Deep Vein Thrombosis
 - PE = Pulmonary Embolism
 - o ASE = Arterial Systemic Embolism
 - TIA= Transient Ischemic Attack.
- · Date and Time of Thrombotic Event
- Time to Thrombotic Event: Time elapsed from first dose of and examet treatment to the Date time of TE. Time to thrombotic events will be calculated in hours and days. Time to Thrombotic Event will also be presented as categorical variable. The following categories will be used: 0-12 hours; >12 hours and < 4 days; 4 to 30 days.

Per correspondence with FDA during label negotiations prior to FDA approval of the label supplement on 06 March 2020, an additional definition of Thrombotic Events includes the following list of adverse event terms:

- "Acute myocardial infarction"
- "Myocardial infarction"
- "Myocardial ischaemia"
- "Troponin increased"
- "Troponin T increased"
- "Cardiac arrest"
- · "Cardio-respiratory arrest"
- "Cardiac failure"
- "Cardiac failure congestive"
- "Right ventricular failure"
- "Cardiac ventricular thrombosis"
- "Cerebrovascular accident"

- "Death"
- "Deep vein thrombosis"
- "Embolism venous"
- "Venous thrombosis limb"
- "Intracranial venous sinus thrombosis"
- "Ischaemic hepatitis"
- "Pulmonary embolism"
- "Acute respiratory failure"
- "Respiratory failure"
- "Embolic stroke"
- "Ischaemic stroke"
- "Sudden death"

- · "Cardiogenic shock"
- "Cerebellar infarction"
- "Cerebellar ischaemia"
- "Cerebral infarction"

- "Transient ischaemic attack"
- "Ventricular tachycardia" "Iliac artery occlusion" "Heparin-induced thrombocytopenia"

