5.17.2. Changes to the Analysis Plan

This analysis plan is an update to version 3.0 (09 August 2019). The main changes to version 3.0 of the Statistical Analysis Plan are:

- 1) Remove stratification of Generation 1 and 2 from all analyses
- Include an extra definition and summary of Thrombotic Events using a broader list of preferred terms, per FDA request
- 3) Reclassify Urinary Bleeds from the "GI" category to the "Other" category
- 4) Pre-specify an analysis of the
 - a. correlation between reversal of anti-fXa activity with effective hemostasis, and
 - b. correlation between reversal of anti-fXa activity with mortality

Previous Changes to SAP

The previous analysis plan was an update to versions 1.0 (30 October 2018) and 2.0 (21 November 2018). The main purpose of changes to the versions 1.0 and 2.0 of the Statistical Analysis Plan was to accommodate additional patients treated with edoxaban and patients in Japan, and to align the SAP with the last version of the protocol (i.e., amendment 5 and 6).

The main change to the SAP (as in the protocol) regards the definition of efficacy evaluable patient population to include requirement of a minimum anti-fXa activity level for edoxaban as follows:

The Efficacy Population will include all patients in the Safety Population who meet all of the following criteria:

- · Are determined by the EAC to meet the clinical bleeding inclusion criteria.
- Have a baseline anti-fXa level
- Baseline anti-fXa level of at least 75 ng/mL for apixaban and rivaroxaban, 40 ng/mL for edoxaban, or 0.25 IU/mL for patients receiving enoxaparin.

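### SAP 5.14 tests the on-treatment anti-fXa nadir, not the decrease named in the secondary objective, and SAP 5.17.2 calls the new models pre-specified without disclosing the departure from the protocol

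*SAP*

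**What the plan says.** Protocol 2.2 sets the secondary objective: "To assess the relationship between decrease in anti-fXa activity and achievement of hemostatic efficacy in patients receiving a FXa inhibitor". Protocol 11.5.3 gives the purpose as "to establish change in anti-fXa activity as a predictor of achievement of hemostatic efficacy". Protocol 11.5.6 makes this a ROC analysis: "For each potential cut point of a percent change in anti-fXa activity, the sensitivity and specificity of that cut point" is calculated against hemostatic success, the area under the curve is reported, and a cut point is taken from the data: "The Minimum Clinically Important Difference (MCID) of percent decrease in anti-fXa activity will be derived". The synopsis names the ROC as the primary tool. Protocol 11.5.7 adds the mean and median percent decrease by hemostatic outcome, and the cumulative distribution function (CDF) in each outcome group.

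SAP 5.14 opens by restating the objective as change from baseline. It then argues that the level reached early on matters more than the size of the fall, and concludes: "Therefore, the on-treatment nadir value will be used in the analysis". Four logistic models follow:

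- Models 1, 2 and 4 use an indicator for nadir below a threshold (30 ng/mL for the direct inhibitors, 0.10 IU/mL for enoxaparin).
- Model 3 uses log nadir.

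An area under the ROC curve with 95% CI is kept, but for these models. SAP 4.4 still lists percent change among the secondary measures.

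SAP 5.17.2, describing changes since version 3.0 of 09 August 2019, has the item "4) Pre-specify an analysis of the", followed by the correlation of reversal with hemostasis and with mortality. In the same SAP version, section 1.0 says "analysis will be performed on all N=477 locked patients in the database", and section 4.6.8 mentions regulatory correspondence "prior to FDA approval of the label supplement on 06 March 2020".

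**The concern.** Two things do not fit together.

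First, the predictor in the models is not the one in the objective. Nadir is the product of where the patient started and how much was reversed. A model with nadir alone cannot say which of the two is related to hemostasis, yet the objective asks about the second. If patients with high baseline levels bleed worse for that or any related reason, the nadir models can show a relationship with no contribution from the decrease.

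Second, calling the models pre-specified invites the reader to give them the weight of a plan fixed before the data. The SAP text suggests that they were added late, and the change list does not say that they replace the protocol's predictor. A report written from this SAP could present a nadir result as the planned answer to the protocol's secondary objective.

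**Working it through.** **The plan's own figure.** No sample size or power is given for the secondary analysis. The only stated figure, 162 evaluable patients for 80% power (61% against 50%), does reproduce. With an exact binomial test, at least 94 of 162 responders are needed, the one-sided error is 0.0246 and power is 0.805. The point here does not depend on it.

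**What a nadir threshold means as a decrease.** Nadir = baseline × (1 − D), where D is the fractional decrease. The percent decrease needed to reach a threshold T is therefore 100 × (1 − T / baseline).

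| Baseline | Source | Decrease needed |
|---|---|---|
| 40 ng/mL | edoxaban floor, SAP 5.2.2 | 100 × (1 − 30/40) = 25% |
| 75 ng/mL | apixaban and rivaroxaban floor, SAP 5.2.2 | 100 × (1 − 30/75) = 60% |
| 100 ng/mL | illustrative | 70% |
| 400 ng/mL | illustrative | 92.5% |
| 950 ng/mL | upper cap, SAP 5.5.1 | 96.8% |
| 0.25 IU/mL | enoxaparin floor, SAP 5.2.2 | 100 × (1 − 0.10/0.25) = 60% |
| 1.0 IU/mL | illustrative | 90% |

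The two predictors can rank patients in opposite ways. A 61% decrease from 75 ng/mL gives 75 × 0.39 = 29.3, coded as below threshold. A 95% decrease from 950 ng/mL gives 950 × 0.05 = 47.5, coded as not below.

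Model 3 does not escape this. Log nadir = log baseline + log(1 − D), so one coefficient is forced on both parts.

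**Can baseline alone produce a nadir result?** The documents give no distributions, so this is an illustration under assumptions:

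- direct inhibitors only
- log-normal baseline with median parameter 150 ng/mL and log-SD 0.6, restricted to at least 75 and capped at 950
- median decrease 90% (log-SD 0.8 for the remaining fraction), nadir not below 4
- response about 61%
- percent decrease has no effect on hemostasis
- the odds of hemostasis fall by a stated factor per doubling of baseline
- 600 simulated trials per row.

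The larger n is 477 × (1 − 0.30 − 0.05) = 310, using the protocol's exclusion estimates.

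| n | Fall in odds per doubling of baseline | Nadir < 30 test significant | Percent-decrease comparison significant |
|---|---|---|---|
| 162 | none | 4.8% | 4.8% |
| 162 | factor 1.5 | 12.3% | 4.7% |
| 162 | factor 2 | 25.7% | 3.7% |
| 310 | none | 6.0% | 6.0% |
| 310 | factor 1.5 | 17.7% | 5.7% |
| 310 | factor 2 | 40.3% | 5.3% |

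The area under the ROC curve stays at about 0.50 for percent decrease. It rises to 0.54 to 0.57 for nadir when baseline matters.

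**Timing.** The change list is relative to 09 August 2019, and this SAP version cites an approval dated 06 March 2020 and speaks of locked patients. The analyses are therefore presented as additions made after version 3.0, in a text finalised no earlier than March 2020. The date of lock is not given.

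**The case against.** The case for the SAP has real content.

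- **The threshold is not arbitrary.** SAP 5.14 takes 30 ng/mL from two sets of guidance, and the protocol's own figure note in 1.4.4 uses the same value as an estimated non-effective level. A fixed external cut point is less data-driven than the one that protocol 11.5.6 would derive. This stands, but it defends the cut point and not the change of predictor.
- **A threshold was foreseen.** Protocol 11.5.7 lists a threshold of anti-fXa activity, with percent and absolute reduction, among parameters to be considered. This stands. The fault is that a supplementary parameter was promoted and the main one left out.
- **Pooling.** SAP 5.14 says levels cannot be combined across inhibitors, hence the indicator. Percent change carries no unit and is already the first primary endpoint, so this reason does not require dropping it.
- **The examples are chosen.** They show what can happen, not how often. Even between baselines of 100 and 400 ng/mL, however, the decrease needed runs from 70% to 92.5%.

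Some stronger readings are tempting, but the documents do not support them:

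- A reader might infer that the predictor was picked after results were seen. No lock date, signature date or text of version 3.0 is available. The earlier submissions in SAP 3.5 are described only as descriptive. Odds-ratio tables for this relationship already stand in a table list that is declared not to be updated.
- A reader might infer that percent change is examined nowhere. SAP 4.4 keeps it, and sample table 14.2.2.6 sets hemostatic efficacy against percentage reduction.
- A reader might apply the post hoc label of SAP 5.15.1.11. That section covers only confounder-adjusted analyses deferred to an addendum.
- A reader might count the likelihood-ratio tests as independent chances of a false positive. The models share patients and outcome, two are sensitivity analyses and one is a subset analysis, and SAP 5.7 treats secondary analyses as exploratory.

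**Conclusion.** The point holds as a mismatch between objective and analysis, and as an unsupported label. No model in SAP 5.14 contains percent change, absolute change or baseline level. The protocol's percent-change ROC with derived cut point, its comparison by outcome and its CDF plots are absent from that section. On the documents' own floors and cap, one 30 ng/mL nadir stands for a decrease of anywhere from 25% to 96.8%, so the models do not answer the question that 5.14 itself restates. The simulated rates depend on the assumed distributions and on baseline being related to hemostasis. They show the direction of the risk, not its size in this trial.

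On the label, the text shows analyses added after version 3.0, in a version that mentions a locked database and March 2020, with no word that the predictor departs from the protocol. That is enough to question the wording. It does not establish the order of lock, results and choice of predictor.

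Both primary endpoints and their conclusions are unaffected. This should be corrected, but it does not threaten the trial's main result.

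**What to change.** In SAP 5.14, make the protocol's analyses the main secondary analysis: the percent-change ROC with its area and 95% CI, the CDF plot, and percent decrease compared by hemostatic outcome. Keep Models 1 to 4, and the mortality model in 5.16.3, as supplementary. A supporting model that includes baseline level would separate the two components of nadir at no extra data cost.

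In SAP 5.17.2:

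- replace *Pre-specify* with *Add*
- give the date of the addition relative to database lock
- label the models post hoc if they were added after lock
- state that the predictor departs from protocol 11.5.6 and 11.5.7, and why.

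A separate detail can be settled in the same edit. SAP 5.5.1 replaces enoxaparin values below 0.10 IU/mL with 0.10, so an indicator for values strictly below 0.10 can never be met if it is applied after that replacement. The order or the inequality needs stating.

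The cost is SAP wording and a few outputs that the protocol already describes, from data already collected. The nadir models may lose the pre-specified label, but nothing needs to be removed.
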